 - c. Symptomatic or documented congestive heart failure that meets New York Heart Association (NYHA) Class III to IV definitions (see Appendix 6);
 - d. History of stroke within the last 6 months prior to screening

Inclusion of Women and Minorities

Both men and women of all races and ethnic groups are eligible for this trial.

Treatment Plan

Patients will be treated with TGR-1202 at a dose of 800 mg daily from day 1 to 28 on a 28-day cycle.

Duration of Treatment

Patients will be treated until one of the following events occurs:

- Disease progression
- Unacceptable adverse event(s)
- Withdrawal of consent
- Changes in the patient's condition that render continuation of the study drug unacceptable in the judgment of the treating physician
- An event that in the judgment of the treating physician warrants discontinuation of therapy.
- Patient withheld study drug for >28 days

Sample Size

The study will accrue a total of up to approximately **20 patients**.

Safety

Patients will be monitored carefully for the development of AE. AE will be evaluated according to criteria outlined in the National Cancer Institute (NCI) Common Terminology Criteria for Adverse Events (CTCAE), version 4.0.

Efficacy Outcome

Patients will be monitored for clinical and/or radiographic evidence of disease response. Response will be evaluated using clinical parameters, CT or PET/CT scan (PET/CT scan is preferred), and bone marrow or other tissue biopsy, according to the *Updated Recommendations for Evaluation, Staging, and Response Assessment for Hodgkin and Non-Hodgkin Lymphoma: The Lugano Classification.* (Cheson et al., 2014b)

Figure 1: Study Plan Flow Chart

[figure not shown]

Figure 2. Pharmacokinetics (PK) schedule

Pharmacokinetic studies

Cycle 1, days 1 and 15; cycle 2 , day 15; cycle 4, day 15

[figure not shown]
[figure not shown]

Figure 3. Pharmacodynamic (PD) Schedule

Pharmacodynamic studies on peripheral blood*

Cycle 1, days 1 and 15; cycle 2, day 15; cycle 4, day 15

Pharmacodynamic studies on tumor cells, blood cells, and buccal fibroblasts*

Screening, Cycle 2, day 15 (mandatory); cycle 4, day 15 (optional); end of treatment/POD (optional)

[figure not shown]
[figure not shown]

Figure 4. Study schema

¹ Includes tumor cells, blood cells, and buccal fibroblasts; tumor tissue includes nodal or extranodal tumor tissue that can be visualized and/or palpated + bone marrow aspiration and biopsy if bone marrow positive for lymphoma; ²

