3. PATIENT SELECTION

Inclusion Criteria

1. Histologically proven diagnosis of grade 1, 2, or 3A FL
2. The diagnosis of relapsed FL must have been made within the last 6 months of screening if no other treatment is given for the FL in the interim; if an interim treatment is given within the last 6 month, re-biopsy will be required even if there is already a biopsy proven relapsed FL within the last 6 months.
3. Pre-treatment biopsy must establish the diagnosis AND have enough remaining tissues to satisfy the mandatory research studies.
4. Relapse following first line immunotherapy or chemoimmunotherapy. There is no upper limit to the number of therapies received prior to study entry. Prior therapies may include high-dose therapy with autologous stem cell rescue.
5. Measurable disease according to the Lugano classification (Cheson et al., 2014a). See Appendices 1 and 2.
6. Lymphoma that is amenable to safe pre-treatment and post-treatment biopsy. The safety of the procedures will be determined by the treating physician and the surgeon or other proceduralist, in consultation with the PI, and in accordance with standard clinical practice. Acceptable sites of disease include, for example: (1) palpable tumor mass that is accessible under direct visualization or sonogram, (2) non-palpable tumor tissue that is accessible for biopsy under CT or sonogram guidance, (3) bone marrow.
7. Age ≥ 18 years.
8. ECOG performance status ≤ 2 (see Appendix 3)
9. Patients must have adequate organ and marrow function as defined below:
 - a. absolute neutrophil count $\geq 1,000/\text{microliter}$
 - b. platelet count $\geq 50,000/\text{microliter}$
 - c. bilirubin $\leq 1.5X$ institutional upper limit of normal
 - d. aspartate transaminase (AST, SGOT)/alanine transaminase (ALT, SGPT) $\leq 3.0X$ institutional upper limit of normal
 - e. Serum creatinine $\leq 2.0X$ institutional upper limit of normal or creatinine clearance $\geq 50 \text{ mL/min}$ (according to the Cockcroft and Gault equation).
10. Negative serum pregnancy test within 7 days prior to Cycle 1/Day 1 for women of childbearing potential

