11. MEASUREMENT OF EFFECT

The primary objective of this study is to evaluate the ORR of the study drug. Patients with measurable disease will be assessed by standard criteria. Patients will be re-evaluated at the end of cycle 2 and cycle 6, thereafter every 4 months, or every 6 months if a CR is achieved. Response will be evaluated with physical exam, computerized tomography (CT) and tissue biopsies as defined in the 2014 Lugano classification.(Cheson et al., 2014b) PET/CT is optional, but strongly encouraged.

Evaluation of response:

Definitions

Evaluable for toxicity: All patients will be evaluable for toxicity starting from Day 1 of Cycle 1.

Evaluable for objective response: Patients who have received at least 1 cycle of therapy, and have had their disease re-evaluated will be considered evaluable for response. These patients will have their response classified according to the definitions stated below (Table 3). Patients who exhibit objective disease progression prior to the end of cycle 1 will also be considered.

Disease Parameters

Measurable disease. Measurable lesions are defined as those that can be accurately measured in two dimensions (longest diameter to be recorded) as ≥ 20 mm with conventional techniques (PET/CT, MRI, x-ray) or as ≥ 10 mm with spiral CT scan. All tumor measurements will be recorded in millimeters (or decimal fractions of centimeters). Tumor volume will be recorded as the sum of the product of the diameters (SPD) of the largest predominant target lesions (for sites of measurable disease, see Appendix 7).

FDG avidity is based on comparison with background tissues. There is no specific SUV cut-off value that is considered indicative of response.

Non-measurable disease (evaluable disease). All other lesions (or sites of disease), including small lesions (<10 mm using spiral CT scan), are considered non-measurable disease. Bone lesions, ascites, pleural/pericardial effusions, lymphangitis cutis/pneumonitis, inflammatory breast disease, abdominal masses (not followed by CT or MRI), and cystic lesions are all nonmeasurable.

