Target nodes/nodal masses, extranodal lesions	Score 4 or 5 with no significant change in FDG uptake from baseline at interim or end of treatment	
 - $\leq 50\%$ decrease from baseline in SPD of up to 6 dominant, measurable nodes and extranodal sites; - no criteria for progressive disease are met
Non-measured lesion	Not applicable	No increase consistent with progression
Organ enlargement	Not applicable	No increase consistent with progression
New lesions	None	None
Bone marrow	No change from baseline	Not applicable
Progressive disease	Progressive metabolic disease	Progressive disease requires at least 1 of the following:
Individual target nodes/nodal Masses	Score 4 or 5 with an increase in intensity of uptake from baseline and/or	PPD progression

Extranodal lesions	New FDG-avid foci consistent with lymphoma at interim or end-of-treatment assessment	An individual node/lesion must be abnormal with: 
 - $LDi > 1.5$ cm and - Increase by $\geq 50\%$ from PPD nadir and - An increase in LDi or SDi from nadir - 0.5 cm for lesions ≤ 2 cm - 1.0 cm for lesions > 2 cm 
In the setting of splenomegaly, the splenic length must increase by $> 50\%$ of the extent of its prior increase beyond baseline (eg, a 15-cm spleen must increase to > 16 cm). If no prior splenomegaly, must increase by at least 2 cm from baseline. New or recurrent splenomegaly

Non-measured lesion	None	New or clear progression of preexisting non measured lesions
New lesions	New FDG-avid foci consistent with lymphoma rather than another etiology (eg, infection, inflammation). If	
 - Regrowth of previously resolved lesions - A new node > 1.5 cm in any axis
	uncertain regarding etiology of new lesions, biopsy or interval scan may be considered	
 - A new extranodal site > 1.0 cm in any axis; if > 1.0 cm in any axis, its presence must be unequivocal and must be attributable to lymphoma - Assessable disease of any size unequivocally attributable to lymphoma
Bone marrow	New or recurrent FDG-avid foci	New or recurrent involvement

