13. STATISTICAL CONSIDERATIONS

Study Design/ Primary Endpoints

This is a phase 2 study of oral TGR-1202 in patients with relapsed or refractory follicular lymphoma. (See figure 1 for study plan flow chart)

Sample Size/Accrual Rate

The phase II will allow for a total accrual of 20 patients.

We estimate accrual of an average of 1-3 patients per month, with a goal of completing accrual within 12 months.

Based on the phase I study of TGR-1202, the ORR for TGR-1202 will be 60%. The ORR is 33% based on historical control drugs, such as lenalidomide. We estimate that 20 patients will be needed to have a power of 87% to reject the null hypothesis that $ORR=0.33$ in favour of alternative hypothesis $ORR=0.6$ with one side type I error rate of 0.10.

Analysis of Primary and Secondary Endpoints

Disease and patient characteristics at baseline will be summarized using descriptive statistics. For qualitative variables, frequency distributions and proportions will be provided; for quantitative variables, summary statistics (e.g., mean, median, quartiles, standard deviations, etc) and graphical

displays (e.g., box plots) will be used. Overall response rates will be measured upon completion of the study with exact 95% confidence intervals.

REFERENCES:

Ansell, S.M., Witzig Te Fau - Kurtin, P.J., Kurtin Pj Fau - Sloan, J.A., Sloan Ja Fau - Jelinek, D.F., Jelinek Df Fau - Howell, K.G., Howell Kg Fau - Markovic, S.N., Markovic Sn Fau - Habermann, T.M., Habermann Tm Fau - Klee, G.G., Klee Gg Fau - Atherton, P.J., Atherton Pj Fau - Erlichman, C., *et al.* (2002). Phase 1 study of interleukin-12 in combination with rituximab in patients with B-cell non-Hodgkin lymphoma.

Armitage, J.O. (1993). Treatment of Non-Hodgkin's lymphoma. *N Engl J Med* 328, 1023-1300.

Baiocchi, R.A., Alinari L Fau - Lustberg, M.E., Lustberg Me Fau - Lin, T.S., Lin Ts Fau - Porcu, P., Porcu P Fau - Li, X., Li X Fau - Johnston, J.S., Johnston Js Fau - Byrd, J.C., Byrd Jc Fau - Blum, K.A., and Blum, K.A. (2011). Phase 2 trial of rituximab and bortezomib in patients with relapsed or refractory mantle cell and follicular lymphoma.

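### Measurable disease starts at 20 mm on PET/CT but 10 mm on spiral CT, so where PET/CT replaces CT the target lesions, and sometimes a CT-criteria PR, can depend on the scan

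*Combined protocol and SAP*

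**What the plan says.** All references are to the combined protocol and SAP.

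- **Size limit.** Section 11 (Disease Parameters) sets measurability at or above "20 mm with conventional techniques (PET/CT, MRI, x-ray) or as" at or above 10 mm on spiral CT. Lesions that do not qualify are non-measurable.
- **Choice of scan.** The synopsis (Efficacy Outcome) provides for "CT or PET/CT scan (PET/CT scan is preferred", in its words. Screening item 7 in Section 4 lists CT, with PET/CT optional but preferred. The Section 10 calendar row and its footnote f allow PET/CT in place of CT or in addition to it. Section 11 strongly encourages PET/CT.
- **Use of the limit.** Under Section 11 (Target lesions), measurable lesions, to a maximum of six, become targets. Their baseline SPD is the reference for response by CT criteria. In the CT column of Table 3, PR is a fall of at least 50% in SPD. The metabolic column has no SPD cut.
- **Other size limits.** For progression, the CT column of Table 3 states "An individual node/lesion must be abnormal with" a longest diameter above 1.5 cm. It also sets nodal CR at 1.5 cm or less.
- **Eligibility.** Inclusion criterion 5 (Section 3) asks for "Measurable disease according to the Lugano classification" and points to Appendices 1 and 2. These are staging tables and give no size limit for measurability.
- **Design.** Section 13 states "The phase II will allow for a total accrual of 20 patients", with ORR as the primary endpoint.

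**The concern.** The size limit is tied to the type of scan, and the stricter limit goes with the preferred scan. Two patients with the same disease can therefore have different target lists and different baseline SPDs because one had PET/CT and the other spiral CT. The SPD is the denominator of the CT-criteria response, so the difference can reach the primary endpoint. Nothing says whether the CT component of a PET/CT counts as a spiral CT.

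The limits also disagree with the response table. A 16–19 mm node on PET/CT is large enough to be abnormal for progression but too small to be a response target. A 10–15 mm node on spiral CT can be a target although it already meets the nodal size for CR at baseline.

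Eligibility may be touched as well. The appendices that criterion 5 points to contain no size, which leaves Section 11 as the only explicit definition of measurable disease in the document.

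**Working it through.** **1. The plan's own figure.** Section 13 assumes that "the ORR for TGR-1202 will be 60" per cent and that "The ORR is 33% based on historical control drugs, such as lenalidomide", and estimates that "20 patients will be needed to have a power of 87% to reject the null hypothesis" at one-sided alpha 0.10. It states no critical value. With X ~ Binomial(20, p), the smallest r with P(X ≥ r | 0.33) ≤ 0.10 is r = 10:

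- P(X ≥ 10 | 0.33) = 0.087
- P(X ≥ 10 | 0.60) = 0.872, which reproduces the 87%

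One patient is 1/20 = 5 points of ORR, and the decision turns between 9 and 10 responders.

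**2. Can the limit change PR?** The documents give no lesion data, so these lesions are assumed. Baseline: 25×20, 22×20 and four of 18×15 mm, six in all.

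- SPD under the 20 mm limit: 500 + 440 = 940 mm²
- SPD under the 10 mm limit: 940 + 4×270 = 2020 mm²

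| Follow-up | 20 mm limit | 10 mm limit |
|---|---|---|
| A. Large nodes to 17×14 and 15×13, small unchanged | 1 − 433/940 = 53.9% fall, PR | 1 − 1513/2020 = 25.1% fall, SD |
| B. Large nodes to 19×15 and 17×14, small to 5×5 | 1 − 523/940 = 44.4% fall, SD | 1 − 623/2020 = 69.2% fall, PR |
| C. Every diameter × 0.70 | 1 − 0.70² = 51.0% fall, PR | 51.0% fall, PR |
| C′. Every diameter × 0.72 | 1 − 0.72² = 48.2% fall, SD | 48.2% fall, SD |

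The limit can change the result in either direction, but only when small and large lesions shrink unequally.

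**3. How much small disease is needed?** Let unchanged 10–19 mm lesions hold a share w of baseline SPD under the 10 mm limit. PR then requires the larger lesions to shrink by 50%/(1 − w):

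- w = 5%: 52.6%
- w = 25%: 66.7%
- w = 50%: 100%

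Where small nodes are a minor share, the limit hardly matters.

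**4. How often?** Simulation with assumed inputs:

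- 2–8 nodes per patient; log-normal longest diameter, log-SD 0.4; short axis 0.75 of the long axis
- log ratio of follow-up to baseline product with mean −0.5 or −0.7, and SD 0.35 both between and within patients
- up to six largest qualifying lesions as targets; PR at an SPD ratio of 0.5 or less

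| Median node | Gross PR disagreement | Net ORR difference | Measurable only under the 10 mm limit |
|---|---|---|---|
| 15 mm | 9–10% | about 2–4 points | about 30% |
| 20 mm | 5–6% | about 1–2 points | about 7% |
| 30 mm | about 1% | under 0.5 point | under 1% |

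Disagreement and net difference are among patients measurable under both limits. The net difference favours the 20 mm limit (more PRs) in every setting. It compares all patients under one limit with all under the other, so mixed use gives less. At a 20 mm median, 1–2 points of 20 patients is 0.2–0.4 of a patient.

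**The case against.** Several points on the other side have force.

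- **Eligibility.** A reader might infer that the scan decides who may enter. The documents do not show that. Criterion 5 cites Lugano, not Section 11, and screening lists CT as the base scan. The two limits are also joined by an or, so a 10–19 mm lesion seen on spiral CT qualifies even if PET/CT is done too. What stands is that eligibility may be affected when PET/CT replaces CT, because no other explicit size is given. Nothing ties scan type to centre.
- **Response.** A reader might infer that the same shrinkage becomes PR or SD according to the scanner. Uniform shrinkage gives the same answer under both limits. Six larger targets would leave no room for small ones. If the metabolic column governs PET/CT patients, the SPD does not determine PR. However, the plan does not say which column governs, and it still builds a baseline SPD when PET/CT is done.
- **Same-method rule.** Section 11 requires the same technique for each lesion at baseline and follow-up. That limits switching within a patient. It does not remove differences between patients or say which limit applies.
- **Size of the effect.** Reading 5–6% disagreement as one patient in 20 lost or gained overstates the effect on ORR, because changes in opposite directions partly cancel. The simulation also takes the largest lesions, whereas Section 11 prioritises FDG avidity when PET/CT is done. The 30% figure needs a median node as small as the nodal CR size.
- **Rationale for two limits.** Section 11 allows cuts up to 10 mm for CT, PET/CT and MRI but asks for 5 mm reconstruction on spiral CT. Each size limit is twice its slice thickness. This may explain the rule, but the limit follows modality, so a thin-slice PET/CT still gets 20 mm. A change to the limit must therefore also change the slice rule.

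**Conclusion.** The concern holds in a limited form. Section 11 as written lets the target set, and so the baseline SPD, depend on whether PET/CT replaces CT. A CT-criteria PR can follow, given three conditions: 10–19 mm lesions among the six or fewer targets, uneven shrinkage, and use of the CT column. Neither limit agrees with the 1.5 cm node limit in Table 3. An effect on eligibility is possible but not established.

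Under the assumed lesion data, gross PR disagreement is about 5–6% at a 20 mm median node (range 1–10%), and the net ORR shift is about 1–2 points (range under 0.5 to about 4). These figures indicate scale; they are not estimates for this trial. One changed patient matters only if the count falls at 9 or 10 of 20, which is true of any design this small. The sample size and the 87% power need no revision. The inconsistency is worth correcting because it is in the stated rule and bears on the primary endpoint.

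**What to change.** 1. In Section 11, take PET/CT out of the 20 mm category. State one size limit per lesion type, read on the CT component whichever scan is used, and consistent with Table 3. Table 3 already uses 1.5 cm for nodes and 1.0 cm for new extranodal sites. These serve progression and new lesions, so adopting them for measurability should be stated explicitly.
2. Apply the 5 mm spiral-CT reconstruction rule to the CT component of PET/CT.
3. Cite the same limit in inclusion criterion 5, in the synopsis and Section 3.
4. Apply the rule prospectively. For patients already enrolled, report a sensitivity ORR with targets re-derived from the baseline CT component by a reader unaware of follow-up. Section 11 does not require measurement of non-target lesions, so follow-up scans must be re-measured for any lesion added. Re-selecting targets for the primary analysis in an open-label trial could itself introduce bias.

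The cost is a few sentences of amendment and some re-measurement. A few target lists or eligibility classifications would change.

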Tests performed within 29 days prior to the date of written informed consent may be accepted as study screening tests provided that these are considered part of standard care.

The initial informed consent form and all subsequent revised written informed consent forms, as well as any amendment or additional written information regarding the study is contingent on the IRB approval. The patient or his/her legally accepted representative will be informed in a timely manner if new information becomes available that may affect the patient's willingness or ability to continue to participate in the trial. The communication of this information will be documented.

Consent for and Use of Tissue Specimens for Correlative Studies

Participation in correlative studies is mandatory for all patients. In addition to the mandatory correlative studies for all patients, there will also be optional correlative studies, which will be performed under a separate section of the informed consent procedure.

Mandatory correlative studies include the following:

For PK studies:

1. Collection of blood at Pre-treatment.
2. Collection of blood at 4h post-treatment on C1D1, C1D15, C2D15 and C4D15.

For PD studies:

1. Collection of blood at Pre-Treatment (total approx.3ml).

Collection of blood at 4h post-treatment on C1D1, C1D15, C2D15 and C4D15 (total approx. 12ml).

The studies will include T cell panel such as T-reg, expression of CD47 and PD-L1, cytokines such as IL-10 and IL-12, and PI3K targeting.

2. Collection of tumor tissues, blood cells, and buccal fibroblasts pre-treatment and 4-8h post-treatment on C2D15.

The studies will include whole exome sequencing, and the levels/activity of c-Myc, 4E-BP1, CK1, and PI3K.

Optional correlative studies are listed below:

Collection of tumor tissues and buccal fibroblasts 4-8h post-treatment on C4D15, at Progression of Disease, and at End of Treatment.

The studies will include whole exome sequencing, and the levels/activity of c-Myc, 4EBP1, CK1, and PI3K.

Registration Process

The Study Coordinator will verify eligibility and complete the registration process, by:

- Assigning a patient study number

- Registering the patient on the study
- Confirming registration with the principal investigator

Screening

Unless otherwise specified, the following procedures and evaluations will be performed as noted in the study calendar (Section 10) prior to the start of study drugs (cycle 1, dose 1):

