Fine Needle Aspirations (FNA): A series of FNAs will be performed on palpable tumors in consenting patients as a function of drug exposure.

Tumor Tissue Biopsies: The biopsies will be performed by a surgeon or an interventional radiologist, as appropriate. If multiple lymph nodes are available, the safest lymph node will be selected. A cytopathologist will evaluate the biopsy for tumor cells microscopically at the time of the biopsy. Correlative studies will be performed on de-identified tissue samples. Tissue will be labeled only with the protocol-specific unique identifier.

Bone Marrow Biopsy: a bone marrow aspirate and biopsy will be performed pre-treatment if necessary to determine the stage of the disease.

Handling of Specimens

Specimens required for clinical diagnosis will be submitted to Pathology per standard patient care practice.

Research specimens will be handled as explained below:

- Blood will be processed to isolate the serum and mononuclear cells. The specimens may then be used immediately for correlative studies such as flow cytometry or stored for future studies in bulk with all patient samples. Stored samples will be either frozen at -80 degrees or refrigerated at 4 degrees Celsius.
- Bone marrow and other tissue aspirate samples will be processed to isolate the mononuclear cells enriched for viable lymphoma cells. The specimens may then be used for correlative studies such as flow cytometry immediately or stored for future studies in bulk with all patient samples.
- Samples from core biopsy (e.g. bone marrow, skin, lymph nodes or other lymphoid tissue) may be snap frozen in a dry ice/alcohol bath or liquid nitrogen, or processed for the isolation of viable lymphoma cells.
- Fibroblasts will be isolated from buccal swabs, and frozen or refrigerated as above.
- Cellular samples will be used immediately or snap frozen, depending on the type of correlative studies. For example, *ex vivo* pharmacological studies require fresh isolated lymphoma. mRNA and DNA may be extracted from frozen or fixed cellular or tissue specimens.

Biomarker studies

A major goal of this study is to determine the genetic, and biochemical heterogeneity in the follicular lymphoma cells, and discover the effects of distinct cellular and molecular alterations on patient response to TGR-1202. To this end, we will perform the following studies using patient samples:

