Target lesions. All measurable lesions, up to a maximum of 6, that are representative of all involved organs, should be identified as target lesions and measured and recorded at baseline. If PET/CT is performed, target lesions should be selected on the basis of their FDG avidity (High SUV lesions will be prioritized, even if not the largest lesions), size (lesions with the largest SPD diameter) and their suitability for accurate repeated measurements (either by imaging techniques or clinically). An SPD for all target lesions will be calculated and reported as the baseline sum SPD. The baseline sum SPD will be used as reference by which to characterize the objective tumor response based on CT criteria.

Non-target lesions. All other lesions (or sites of disease) including any measurable lesions over and above the 6 target lesions should be identified as non-target lesions and should also be recorded at baseline. Measurements of these lesions are not required, but the presence or absence of each should be noted throughout follow-up.

Methods for Evaluation of Measurable Disease in NHL

All measurements should be taken and recorded in metric notation using a ruler or calipers. All baseline evaluations should be performed as closely as possible to the beginning of treatment and never more than 4 weeks before the beginning of the treatment.

The same method of assessment and the same technique should be used to characterize each identified and reported lesion at baseline and during follow-up. As a general rule imaging-based evaluation is preferred to evaluation by clinical examination when both methods have been used to assess the antitumor effect of a treatment.

Clinical lesions. Clinical lesions will only be considered measurable when they are superficial (e.g., skin nodules and palpable lymph nodes). In the case of skin lesions, documentation by color medical photography that includes a ruler to measure the size of the lesion, is recommended.

CT, PET/CT and MRI. These techniques should be performed with cuts of 10 mm or less in slice thickness contiguously. Spiral CT should be performed using a 5 mm contiguous reconstruction algorithm. This applies to tumors of the chest, abdomen, and pelvis. Imaging of head and neck tumors and those of the extremities will be performed according to institutional specific protocols.

Ultrasound (US) Will not be used for disease assessment

Response Criteria

Response assessment in NHL

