Responses will be evaluated using clinical parameters, CT scan (PET scan is optional) and bone marrow biopsy according to the 2014 Lugano Classification (Cheson et al., 2014a) as outlined in Table 3.

Table 3. Revised Criteria for Response Assessment (Cheson et al., JCO 2014)

Complete	Complete metabolic response	Complete radiologic response (all of the following):
----------	-----------------------------	--

Lymph nodes and extralymphatic sites	Score 1, 2, or 3* with or without a residual mass on 5PS† It is recognized that in Waldeyer's ring or extranodal sites with high physiologic uptake or with activation within spleen or marrow (eg, with chemotherapy or myeloid colony-stimulating factors), uptake may be	Target nodes/nodal masses must regress to ≤ 1.5 cm in LD _i . No extralymphatic sites of disease
--------------------------------------	--	---

	greater than normal mediastinum and/or liver. In this circumstance, complete metabolic response may be inferred if uptake at sites of initial involvement is no greater than surrounding normal tissue even if the tissue has high physiologic uptake	
Nonmeasured lesion	Not applicable	Absent
Organ enlargement	Not applicable	Regress to normal
New lesions	None	None
Bone marrow	No evidence of FDG-avid disease in marrow	Normal by morphology; if indeterminate, IHC negative
Partial	Partial metabolic response	Partial remission (all of the following):
Lymph nodes and extralymphatic sites	Score 4 or 5† with reduced uptake compared with baseline and residual mass(es) of any size	$\geq 50\%$ decrease in SPD of up to 6 target measurable nodes and extranodal sites
Non-measured lesion	At interim, these findings suggest responding disease	When a lesion is too small to measure on CT, assign 5 mm x 5 mm as the default value
Organ enlargement	At end of treatment, these findings indicate residual disease	When no longer visible, 0 x 0 mm. For a node > 5 mm x 5 mm, but smaller than normal, use actual measurement for calculation
New lesions	None	None
Bone marrow	Residual uptake higher than uptake in normal marrow but reduced compared with baseline (diffuse uptake compatible with reactive changes from chemotherapy allowed). If there are persistent focal changes in the marrow in the context of a nodal response, consideration should be given to further evaluation with MRI or biopsy or an interval scan	Not applicable
No response or stable disease	No metabolic response	Stable disease:

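### Under CT-based assessment, a target node that is excised or debulked for biopsy after the baseline scan would count as tumor shrinkage, because no rule takes it out of the SPD

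*Combined protocol and SAP*

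**What the plan says.** All references are to the combined protocol and SAP.

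- **Target lesions (Section 11, Disease Parameters):** "All measurable lesions, up to a maximum of 6, that are representative of all involved organs, should be identified as target lesions". There is no exception for a lesion chosen for biopsy.
- **Reference value (same section):** "The baseline sum SPD will be used as reference by which to characterize the objective tumor response based on CT criteria".
- **Partial remission on CT (Table 3):** at least a 50% "decrease in SPD of up to 6 target measurable nodes and extranodal sites". The same table gives the value for a lesion that has gone: "When no longer visible, 0 x 0 mm". It makes no distinction by reason.
- **Which node is biopsied, and by whom (Section 9, Tumor Tissue Biopsies):** "If multiple lymph nodes are available, the safest lymph node will be selected", and "The biopsies will be performed by a surgeon or an interventional radiologist, as appropriate".
- **Mandatory tissue (Section 4, repeated in Section 9):** "Collection of tumor tissues, blood cells, and buccal fibroblasts pre-treatment and 4-8h post-treatment on C2D15".
- **First response scan (Section 11):** "Patients will be re-evaluated at the end of cycle 2 and cycle 6".
- **Baseline order (Section 10, Study Calendar):** the screening CT and the screening tumor biopsy are both due within 4 weeks of treatment start. Neither is required to come first.

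No section says how a target lesion that has been removed or reduced by biopsy enters the SPD.

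**The concern.** The primary endpoint is ORR by best response in a single-arm trial of 20 patients, so each response call carries weight. In a patient with six or fewer measurable lesions, a measurable node that is biopsied will usually be a target as well. If tissue removal takes away all or much of that node between the baseline scan and a response scan, SPD falls for a reason unrelated to the drug. An excised node stays at zero, so the cycle 6 scan does not undo the effect, and best response keeps any earlier PR. There is no control arm in which the same artefact would show up and cancel.

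**Working it through.** **1. The plan's own figure.** Section 13 gives N = 20, null ORR 0.33, alternative 0.60, one-sided alpha 0.10 and power 87%. No cutoff is printed. By exact binomial:

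- P(X ≥ 10 | n = 20, p = 0.33) = 0.0866
- P(X ≥ 9 | n = 20, p = 0.33) = 0.1818, above 0.10
- P(X ≥ 10 | n = 20, p = 0.60) = 0.8725

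The stated 87% is reproduced by a cutoff of 10 of 20. That cutoff is an inference.

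**2. Timing.** Cycles last 28 days. Cycle 2 day 15 is study day 28 + 15 = 43, and cycle 2 ends on day 56. The gap is 56 − 43 = 13 days. With ±3 days on each visit it runs from 13 − 6 = 7 to about 13 + 6 = 19 days (20 if counted to day 1 of cycle 3).

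**3. Effect on SPD.** Assume k equal-sized target lesions, one excised after the baseline scan and scored 0 x 0 mm. SPD falls by 1/k. A total fall of 50% then needs shrinkage s in the others, where (1 − 1/k)(1 − s) = 0.5, so s = 1 − 0.5k/(k − 1).

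| Targets k | SPD fall from excision | Shrinkage needed in the rest for PR (50% without excision) |
|---|---|---|
| 2 | 50% | 0% |
| 3 | 33% | 25% |
| 4 | 25% | 33% |
| 5 | 20% | 37.5% |
| 6 | 17% | 40% |

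With two equal targets, the SPD part of the PR definition is met with no drug effect. The other parts, such as no new lesions, must still hold.

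**4. Effect on the trial's conclusion.** Take a true ORR of 0.33 and exactly one patient scored PR because of excision.

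- If that patient is scored PR whatever the true status, the other 19 must supply 9: P(X ≥ 9 | n = 19, p = 0.33) = 0.139.
- If that patient is always a true non-responder, 9 true responders in 20 are enough: P(X ≥ 9 | n = 20, p = 0.33) = 0.182. This is the upper limit for one such patient.

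**5. Sensitivity to frequency.** Let q be the share of true non-responders scored PR through tissue removal. The documents give no value, so q is an assumption. The scored ORR is 0.33 + 0.67q.

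| q | Scored ORR | P(X ≥ 10 of 20) |
|---|---|---|
| 0 | 0.330 | 0.087 |
| 3% | 0.350 | 0.122 |
| 5% | 0.364 | 0.150 |
| 10% | 0.397 | 0.236 |

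The 0.10 limit is passed at q of about 1.2%.

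**The case against.** The strongest reply is that the protocol never says nodes are excised. Section 9 names fine needle aspiration and core samples and has a cytopathologist check for tumor cells during the procedure, which suits needle work. The inclusion criteria list image-guided sites and bone marrow. Naming a surgeon identifies an operator, not a technique. This stands: every figure above is for excision, needle or core sampling should change SPD little, and marrow does not enter it.

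Four further limits also stand.

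- **PET-based calls.** PET/CT is preferred, and the metabolic column of Table 3 uses uptake with no 50% SPD threshold. The mechanism belongs to CT-based calls. PET is optional, however, so CT may decide some patients. With PET/CT, targets are also chosen partly for suitability for repeat measurement, which would let a reader avoid a node due for biopsy but does not require it.
- **Not every patient.** Patients who miss 4 or more doses may not have the cycle 2 biopsy, and with more than six measurable lesions the biopsied node need not be a target.
- **Order.** A node removed before the baseline scan never enters the baseline SPD and causes no bias.
- **Confirmation.** Section 11 makes best response depend on confirmation criteria as well as measurement. It does not define them, so they cannot be counted on to catch this.

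A reader might infer that tissue removal will always push ORR upward, or that the trial's real type I error is 18.2%. The documents support neither. The first would need excision or debulking of a target after baseline as a matter of course. The second assumes that one such case occurs and that it falls on a true non-responder.

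**Conclusion.** The gap is real but conditional. When a target node is excised or debulked after the baseline scan and response is called on CT, the written rules score the removal as shrinkage, and nothing in the plan corrects it. With equal-sized targets, excising one lowers SPD by 17% (six targets) to 50% (two targets), or by 100% if it is the only target. One resulting PR moves the false-success chance at a true ORR of 33% from 8.7% to 13.9%, and to 18.2% at most, given the inferred cutoff of 10 of 20. The expected bias cannot be calculated, because the documents do not say how often nodes would be excised, how many patients have few targets, or how many will be assessed by CT alone. It may be negligible if sampling is by needle or core. The point still merits action: the remedy is cheap, and a single call matters with 20 patients.

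**What to change.** Add to Section 11:

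1. Identify the lesion intended for biopsy before target lesions are chosen. Do not make it a target where another measurable lesion exists.
2. If a target lesion is excised or debulked after the baseline scan, drop it from the SPD at baseline and at every later assessment. No PR or CR may rest on its removal.
3. Keep lesions sampled only by needle or core in the SPD, flag them on the CRF, and report a sensitivity ORR that excludes all biopsied lesions.
4. A patient whose only target lesion was excised cannot be counted as a CT-based responder on that basis.

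Items 2 and 3 treat excised and sampled lesions differently on purpose. Dropping every sampled lesion would leave a patient whose sole measurable lesion was needle-biopsied with no SPD and no possible CT-based PR.

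The cost is one paragraph, one CRF field and slightly fewer target lesions in patients with limited disease. Sample size, inferred cutoff and stated power do not change.
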